10.12.2 Efficacy Endpoints

Baseline will be derived for efficacy endpoints within each study period:

- Period 1 baseline:
- NPRS score: Mean of the last five available ratings of daily pain recorded in baseline period 1.

- NPRS score with timepoints: For subjects with NPRS collected at timepoints in baseline and week 4 visits, baseline will be defined as the pre-dose assessment at the respective visit.
- Secondary Efficacy endpoints: Latest measurement taken prior to Day 1 dosing.
- Period 2 baseline:
- NPRS score: Mean of the last five available ratings of daily pain recorded in baseline period 2. If there are less than 5 ratings in baseline period 2, then baseline from period 1 will be considered.
- NPRS score with timepoints: For subjects with NPRS collected at timepoints in baseline and week 4 visits, baseline will be defined as the pre-dose assessment at the respective visit. If pre-dose assessment is missing, then pre-dose assessment from the respective visit in period 1 will be considered.
- Secondary Efficacy endpoints: Latest measurement taken on/after Day 43 and prior to Day 50 dosing. If baseline measurement is missing in period 2, then baseline from period 1 will be considered.

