8.4 Washout (Days 29-42)

The first treatment period will be followed by a washout period of two weeks (Days 29 to 42 inclusive). Subjects will continue their NPRS diary entries each evening, but will not take any IMP.

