9.1 Primary endpoint

Absolute change in mean pain score, using an 11 point NPRS, from baseline to the last week of
each treatment period. Pain is recorded once daily in a subject diary in the evening, and should
reflect the subject's average pain over the last 24 hours

Baseline mean pain for each subject is defined as the mean of the last five available ratings of daily pain, recorded in each baseline period.

End of treatment mean pain for each subject is defined as the mean of the last five available ratings of daily pain, recorded in the last 7 days of each 4 week treatment period.

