7.1 Primary Efficacy Endpoints

1. *Absolute change in mean pain score, using an 11 point NPRS, from baseline to the last week of each treatment period. Pain is recorded once daily in a subject diary in the evening, and should reflect the subject's average pain over the last 24 hours*

Baseline mean pain for each subject is defined as the mean of the last five available ratings of daily pain, recorded in each baseline period.

End of treatment mean pain for each subject is defined as the mean of the last five available ratings of daily pain, recorded in the last 7 days of each 4 week treatment period.

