10.13 Change from Baseline

Change and % Change between Baseline and post-baseline result will be calculated for all efficacy and safety endpoints within each study period as below:

- Change = Result at Day x – Baseline Result
- % Change = _____x100

When baseline NPRS score = 0, % change from baseline will be calculated using an imputed value of 0.1 at baseline. The range of the NPRS score is 0-10; an imputed value of 0.1 is deemed small enough to be close to zero for percentage change calculations. This imputation will not be included in absolute or change from baseline results.

For subjects with NPRS collected at timepoints in baseline and week 4 visits, change and % change from baseline will be calculated using pre-dose values for timepoints 0.5, 1, 2, 4, 6 hours at each visit.

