10.15 Efficacy Endpoints

10.15.1 NPRS Mean Scores

NPRS mean daily score ranging from 0 (no pain) to 10 (worst imaginable pain) will be derived at baseline and weeks 1 to 4 for each treatment period. Baseline mean score is defined in Section 10.12.2. The mean daily pain score each week during treatment is the arithmetic mean of the last 5 available ratings of daily pain recorded in each 7 day period within each treatment period. Standard deviations (SD) of the mean scores will be included in analyses datasets. If a subject has <5 non-missing ratings, the mean score will be set to missing for the respective week.

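### SAP 10.12.2 replaces an incomplete Period 2 NPRS baseline with the Period 1 baseline, leaving valid Period 2 ratings unused and contradicting the period-specific definition

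*SAP*

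**What the plan says.** Protocol 9.1 defines baseline pain as "the mean of the last five available ratings of daily pain, recorded in each baseline period", and SAP 7.1 repeats this. SAP 10.12.2 opens on the same principle: "Baseline will be derived for efficacy endpoints within each study period". For Period 2 it then adds: "If there are less than 5 ratings in baseline period 2, then baseline from period 1 will be considered". No rule in either document uses the one to four ratings that such a subject may have.

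The substituted value is used twice. SAP 10.13 sets "Change = Result at Day x – Baseline Result", and SAP 11.6.1.2 uses the period's baseline as a covariate.

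A treatment week is handled differently (SAP 10.15.1): "If a subject has <5 non-missing ratings, the mean score will be set to missing for the respective week". Nothing is borrowed from the other period.

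For the timed NPRS scores in PK subjects, SAP 10.12.2 says: "If pre-dose assessment is missing, then pre-dose assessment from the respective visit in period 1 will be considered". SAP 12 does not list either rule as a change to the planned analyses.

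**The concern.** A subject with four ratings on Days 43-49 has a usable drug-free baseline, yet the plan replaces it with ratings from Days -7 to -1, seven weeks earlier and before any study drug. The Period 2 change then compares Period 2 pain with a Period 1 starting point, although the trial collects a second baseline to avoid this.

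The problem can arise only in Period 2. Inclusion criterion 7 guarantees at least five ratings before randomisation, and no such requirement applies at Day 50.

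At stake are individual change scores and responder status, some precision in the primary comparison, and bias in the treatment contrast if the problem is uneven between sequences.

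The timed-NPRS rule has a related flaw. SAP 10.3 pairs Visit 4 with Visit 7, so a missing Day 77 pre-dose score is filled from Day 28, after four weeks on the other treatment. SAP 7.2 defines that change against a score taken within the hour before the same dose.

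**Working it through.** **1. The plan's own figure.** Inputs (Protocol synopsis and 13.2): difference 1, SD of change 2, correlation 0.5, two-sided 5%, power 90%, dropout 20%.

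- SD of the within-subject difference = √(2 × 2² × (1 - 0.5)) = 2.0.
- Normal approximation: n = (1.960 + 1.282)² × 2² / 1² = 42.03, rounded up to 43.
- Noncentral t with 43 df: power 0.9000 at n = 44. Then 44 / 0.8 = 55.

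The stated 44 and 55 reproduce, and nothing below changes them.

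**2. How often the rule applies.** The second baseline has seven days. The completion rate is an assumption, with days missed independently; the count is binomial.

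| Days completed | P(fewer than 5 of 7) | Expected of 44 |
|---|---|---|
| 95% | 0.4% | 0.2 |
| 90% | 2.6% | 1.1 |
| 85% | 7.4% | 3.2 |
| 80% | 14.8% | 6.5 |

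P(3 or 4 ratings) = 35p⁴q³ + 35p³q⁴. At p = 0.9 this is 0.0230 + 0.0026 = 0.0255, or 99% of those affected. At p = 0.8 it is 0.1147 + 0.0287 = 0.1434, or 97%.

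**3. The primary model.** Let Y be the week-4 score and B the baseline used. The model is Y - B = βB + period + treatment + subject + error. Moving B across gives Y = (1 + β)B + the same terms. The treatment estimate is therefore the one obtained by modelling Y itself, which the rule leaves untouched. Substitution acts only as error in the covariate.

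This was simulated with 44 subjects, 4,000 trials, true difference -1 and assumed week-to-week baseline SD 0.8, with no shift between baselines. With 20% substituted, the mean baseline-adjusted estimate stayed at -1.00 and its SD rose from 0.302 to 0.312 (0.312 / 0.302 = 1.03).

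Without baseline adjustment, the SD of the difference is √(4 + f·s²), where f is the fraction substituted and s the SD of B2 - B1. For s from 1 to 2 (assumed), power at n = 44 is 0.897-0.886 at f = 5%, 0.893-0.871 at 10% and 0.886-0.841 at 20%.

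**4. When the contrast is biased.** If Period 2 baselines differ from Period 1 by D, the mean Period 2 change shifts by f × D. If this is equal in both sequences, the period effect absorbs it. If it occurs in one sequence only, the contrast shifts by f × D / 2:

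- f = 5%, D = 0.5: 0.0125
- f = 10%, D = 1.0: 0.05
- f = 20%, D = 1.0: 0.10
- f = 20%, D = 1.5: 0.15

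If D is common but missingness is 20% in one sequence and 10% in the other, the shift at D = 1 is (0.20 - 0.10) × 1 / 2 = 0.05.

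The formula is for raw change. In the simulation with f = 20% and D = 1 in one sequence, -1.00 became -0.90 unadjusted and -0.87 with the covariate, so adjustment does not remove this bias. A second simulation, with an assumed slope of 0.7 of week-4 score on baseline and f = 14.8%, gave a shift of 0.06; the formula gives 0.148 / 2 = 0.074.

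**5. One subject.** Baselines 6 (Period 1) and 5 (Period 2), week-4 score 4. SAP rule: (4 - 6)/6 = -33%, a 30% responder. Own Period 2 baseline: (4 - 5)/5 = -20%, a non-responder. With baselines 5 and 6 the error reverses: -20% instead of -33%. The identity in step 3 does not help here, because B is the denominator. McNemar's test and the responder model (SAP 11.6.2.2 and 11.6.2.2.1) contain no baseline term.

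**The case against.** The best defence has three parts.

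- **The SAP may set such a rule.** Protocol 13.1 leaves missing-data methods to it. Protocol 5.2 treats the pain as chronic with no period effect; on that premise an earlier drug-free baseline adds noise, not bias. This stands, and it limits the harm. It does not explain why recorded Period 2 ratings should be ignored.
- **Blinded review can deal with it.** SAP 8.1 defers imputation for the primary endpoint, SAP 9.2 defers exclusions for endpoint completeness and defines the per-protocol set by period, and SAP 11.6.1.2 defers sensitivity analyses. These are real openings for a correction, but a general deferral does not override an explicit rule in 10.12.2.
- **Five ratings is the plan's standard.** A lower minimum departs from the treatment-week rule and from inclusion criterion 7. That is fair, but consistency with the treatment-week rule would mean setting the baseline to missing, not importing one from the other period.

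On timed NPRS, the defence largely succeeds on importance. The rule affects at most 15 subjects and applies only when the score is missing, so no observation is thrown away. The SAP's timepoint model has no treatment term, so no treatment contrast there is distorted.

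**Conclusion.** The rule contradicts the endpoint definition it serves and should be changed. Its likely effect on the primary result is small. With 10-20% of diary days missed independently, about 1 to 7 of 44 subjects are affected. In the baseline-adjusted model the cost is mainly precision, about 3% on the standard error with 20% substituted in the simulation. Bias of about 0.01-0.15 points, against a design difference of 1, needs a baseline shift or missingness that differs by sequence. Completion rates, shifts and SDs are all assumptions. Raw change, percentage change and responder outputs are the more exposed results.

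Two stronger readings are not supported:

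- A reader might infer that any fall in pain between periods passes in full into the treatment difference. It does so for one subject's raw change. In the comparison, a shift common to both sequences goes into the period effect.
- A reader might infer that the entry window makes the Period 1 baseline overstate later pain. The window, 4 to 8, is two-sided. With assumed between-subject SD 1.6 and week-to-week SD 0.8-1.2, the mean excess is +0.07 to +0.13 if the population mean is about 5.5, zero at 6.0, and -0.07 to -0.13 at 6.5. The documents give no such mean, and the effect would be common to both sequences.

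**What to change.** In SAP 10.12.2, before database lock:

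1. Define the Period 2 NPRS baseline as the mean of up to the last five available ratings on Days 43-49, with a stated minimum, for example three.
2. Below the minimum, treat the baseline as missing and handle it in the model by a method named in advance. At 80% completion, P(fewer than 3 of 7) = 0.0043 + 0.0004 = 0.0047, or about 0.2 of 44 subjects.
3. Do not reach back into washout. The ratings exist (Protocol 8.4: "Subjects will continue their NPRS diary entries each evening, but will not take any IMP"), but Days 29-42 lie outside the defined baseline and closer to Period 1 treatment, so any residual effect would differ by sequence.
4. Keep the Period 1 substitution only as a sensitivity analysis, and record the rule in SAP 12.
5. For timed NPRS, set the change to missing when the same-visit pre-dose score is missing.

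The cost is SAP wording and programming; no new data are needed. The drawback is that a few baselines will rest on three or four ratings.

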10.13 Change from Baseline

Change and % Change between Baseline and post-baseline result will be calculated for all efficacy and safety endpoints within each study period as below:

- Change = Result at Day x – Baseline Result
- % Change = _____x100

When baseline NPRS score = 0, % change from baseline will be calculated using an imputed value of 0.1 at baseline. The range of the NPRS score is 0-10; an imputed value of 0.1 is deemed small enough to be close to zero for percentage change calculations. This imputation will not be included in absolute or change from baseline results.

For subjects with NPRS collected at timepoints in baseline and week 4 visits, change and % change from baseline will be calculated using pre-dose values for timepoints 0.5, 1, 2, 4, 6 hours at each visit.

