4.4 Inclusion/Exclusion Criteria

4.4.1 Inclusion Criteria:

Subjects must meet the following criteria to be entered into the study:

1. *Clinical diagnosis of post herpetic neuralgia, with pain persisting for at least 3 months after the onset of herpes zoster rash OR*
2. *Clinical diagnosis of distal painful polyneuropathy due to Type I or Type II diabetes mellitus with:*
 - a) *symmetrical, bilateral pain in the lower extremities for at least 3 months and*
 - b) *diabetes under control for at least 3 months prior to randomisation, as indicated by a glycated haemoglobin level (HbA1c) of $\leq 11\%$ (97 mmol/mol) and on a stable dose of insulin or oral diabetic medication for 3 months prior to screening, and*
 - c) *no change in diabetic medication planned for the duration of the study*

3. *Positive sensory symptoms (mechanical or thermal) associated with neuropathic pain, confirmed by:*
 - a) *painDETECT Questionnaire (PD-Q) and*
 - b) *Clinical assessment, showing signs of neuropathic pain in either a dermatomal (PHN) or distal symmetrical distribution (DPN)*
4. *Aged 18 to 75 years*
5. *Subjects must be sufficiently competent in English to understand the purposes and risks of the study and able to give voluntary written informed consent to participate in the study*
6. *Willing and able to comply with all study procedures*
7. *Completion of at least five NPRS scores during the week preceding randomisation*
8. *An average daily pain score on the NPRS of at least 4 and no more than 8 in the last five diary entries before randomisation*
9. *No more than one score on the NPRS of 9 or more, and no more than one score of 2 or less, in the last five diary entries before randomisation*
10. *Females of child bearing potential must have a negative pregnancy test at Visit 1 (Screening) and at Visit 2 (Day 1) prior to administration of IMP*
11. *Female subjects must be:*
 - a) *of non child-bearing potential [surgically sterilised or post-menopausal (12 months with no menses without alternative medical cause)] OR*
 - b) *not pregnant, breast feeding or planning to become pregnant AND willing to comply with the medically acceptable contraceptive requirements of the study from Screening to at least 28 days after the last IMP administration*

4.4.2 Exclusion Criteria:

Subjects who meet any of the following criteria will be excluded from the study:

1. *Presence of moderate to severe pain from other causes that may confound assessment or selfevaluation of NP*

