11.6.1.1.1 NPRS at timepoints

For per-protocol subjects with NPRS collected at timepoints in baseline and week 4 visits, descriptive summaries of NPRS mean scores, absolute change and % change from baseline results will be presented by study period and total including timepoints 0.5, 1, 2, 4 and 6 hours after the dose of IMP at Visit 2/Visit 5 and Visit 4/Visit 7.

In DDP: Table 14.2.1.3

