11.6.2 Secondary Efficacy analyses

11.6.2.1 Percentage change from baseline in mean NPRS scores

The mixed effects regression model fitted to the absolute change from baseline in mean NPRS scores will be fitted to the percentage change from baseline in mean NPRS scores for both the PP and FAS populations. No sensitivity analyses of missing data patterns will be undertaken.

In DDP: Tables 14.2.2.1 to 14.2.2.2

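### Replacing a zero NPRS baseline by 0.1 can give percentage changes of 1000% or more; one such record at the second baseline could dominate the secondary percentage-change model

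*SAP*

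**What the plan says.** SAP 10.13 sets the rule: "When baseline NPRS score = 0, % change from baseline will be calculated using an imputed value of 0.1 at baseline". Its reason is that "an imputed value of 0.1 is deemed small enough to be close to zero for percentage change calculations". It then limits the rule's reach: "This imputation will not be included in absolute or change from baseline results".

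Percentage change is used in three places:

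- **Weekly means, modelled.** Under SAP 11.6.2.1 the mixed model "will be fitted to the percentage change from baseline in mean NPRS scores for both the PP and FAS populations". Protocol 13.5.1 plans the same comparison.
- **Weekly means, described.** SAP 11.6.1.1 summarises percentage change by week and lists it by subject.
- **Timepoint scores in PK subjects, described.** Under SAP 11.6.1.1.1, "absolute change and % change from baseline results will be presented by study period". The timepoint model in SAP 11.6.1.2.1 uses absolute change from pre-dose.

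Entry requires "An average daily pain score on the NPRS of at least 4 and no more than 8" over the last five diary entries before randomisation (SAP 4.4.1). SAP 10.12.2 sets no minimum for the second baseline or for the single pre-dose ratings. SAP 8.2, on outliers, deals only with laboratory values that carry modifiers. I found no cap, transformation or exclusion for extreme percentage changes.

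**The concern.** Percentage change from zero is undefined. Once a small constant replaces the zero, the size of the result is set by the constant. The SAP's reason runs the wrong way: the closer the substitute is to zero, the larger the distortion. A subject who goes from no pain to mild pain then carries a value many times larger than any subject with an eligible baseline can produce.

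The percentage-change model is tested at the 5% level in both PP and FAS. A least-squares type of model with about 44 subjects has no protection against one value of 1000% or more. At stake is the credibility of that secondary result, or a decision after unblinding to drop the record.

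**Working it through.** **1. Size of the artefact.** The fraction in the SAP 10.13 formula is not legible in the text available to me. I therefore show both readings: numerator (post - 0) or (post - 0.1), each divided by 0.1 and multiplied by 100.

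| Later score | Numerator uses 0 | Numerator uses 0.1 |
|---|---|---|
| 0 | 0% | -100% |
| 1 | 1000% | 900% |
| 2 | 2000% | 1900% |
| 4 | 4000% | 3900% |
| 10 | 10000% | 9900% |

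From a baseline of 4, the possible range is (0 - 4)/4 = -100% to (10 - 4)/4 = +150%.

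**2. Where a zero can occur.**

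- *First baseline, weekly means:* not in an eligible subject, because the mean must be 4 to 8.
- *Second baseline, weekly means:* possible only if all of the last five ratings are 0. With fewer than five ratings, SAP 10.12.2 substitutes the first baseline.
- *PK pre-dose ratings (Days 1, 28, 50, 77):* one rating of 0 is enough, and it affects all five post-dose timepoints at that visit. If a period 2 pre-dose score is missing, the matching period 1 score is used, so a zero can be carried across.

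**3. Effect on a raw mean.** Assumption, not in the documents: 43 subjects average -20% with SD 35. One further record is added.

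- Score 1: (43 × -20 + 1000)/44 = +3.2%, SD about 158.
- Score 2: (43 × -20 + 2000)/44 = +25.9%, SD about 306.
- Score 4: (43 × -20 + 4000)/44 = +71.4%, SD about 607.

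In a timepoint table of 15 PK subjects, a single 2000% value contributes 2000/15 = 133 points to the mean.

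**4. Effect on an adjusted crossover model.** The plan's own sample size reproduces. The SD of the within-subject difference is sqrt(2 × 2² × (1 - 0.5)) = 2, and a paired t-test with n = 44 and a difference of 1 has power 0.900.

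Those inputs were used to simulate 44 subjects. Further assumptions, not in the documents, are:

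- first baseline mean 6, SD 1, held to 4-8;
- second baseline equal to the first plus noise of SD 0.8;
- placebo change -1;
- week 4 only;
- numerator using 0.

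The model adjusted for baseline and period, with subject as a fixed effect (300 runs per scenario). One period 2 baseline was set to 0.

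| Zero-baseline record | Week 4 score | Difference (points) | SE | Power |
|---|---|---|---|---|
| none | - | -16.8 | 5.2 | 0.89 |
| LAT8881 | 1 | -6.3 | 16.9 | 0.02 |
| LAT8881 | 2 | +3.8 | 32.1 | 0.02 |
| LAT8881 | 4 | +29.8 | 61.6 | 0.03 |
| placebo | 1 | -26.3 | 16.6 | 0.32 |
| placebo | 2 | -35.0 | 31.9 | 0.11 |
| placebo | 4 | -56.4 | 62.0 | 0.10 |

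With subject as a random effect (100 runs) the pattern is the same: -17.0 without the record, +9.1 with a LAT8881 record at score 2, and -44.5 with a placebo record at score 2. Power for absolute change stayed between 0.80 and 0.89 in the scenarios tabulated. The SAP's model uses weeks 1 to 4, so one zero second baseline would feed in up to four inflated weekly values, where the simulation used one.

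**The case against.** The best argument against the point concerns reach. The more plausible trigger, a single pre-dose 0 in a PK subject, never enters a percentage-change model. The modelled weekly means need five zero ratings in the third week off IMP, in a condition that protocol 5.2 describes as chronic and treated symptomatically. The documents give no reason to expect even one case. Both limits stand.

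The consequence is also limited. The primary endpoint is absolute change, and SAP 10.13 keeps the 0.1 out of it. Continuous percentage change is not among the twelve secondary endpoints in SAP 7.2, although SAP 11.6.2 places it among the secondary analyses. SAP 8 reports median, minimum and maximum, and the weekly values are listed, so an extreme value would be seen. That protects the descriptive tables in part; it does not protect the model's estimate or p-value.

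A reader might infer that the rule penalises good responders, and so works against LAT8881. The documents do not support that for the modelled endpoint. A subject who reached zero pain after LAT8881 in period 1 receives placebo in period 2, so the inflated value falls on placebo and favours LAT8881. The direction depends on sequence.

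A reader might also infer that every triggered value is in the thousands of percent. A later score of 0 gives 0% or -100%, and values near 1000% need a later score of about 1 or more.

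**Conclusion.** The point holds as a minor one. When the rule is triggered, the value it returns reflects the chosen constant, and nothing in the SAP contains it. One zero second baseline could shift the secondary percentage-change estimate by tens of points either way and remove most of the model's power. The simulated sizes rest on the assumed baselines and on one week 4 record per period; the percentages in step 1 follow from the rule alone. How often a zero second baseline would occur is unknown and probably low.

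The point does not extend to the primary analysis or to the timepoint model, both of which use absolute change.

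There is a further loose end in the 30% and 50% responder flags (SAP 10.16.1). A subject with 0 at baseline and 0 at week 4 is a responder if the change is -100% and a non-responder if it is 0%, so the flag depends on how the formula's numerator is read.

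**What to change.** In SAP 10.13:

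- Delete the 0.1 imputation and set percentage change to missing (undefined) when baseline is 0.
- Count and list the affected records by treatment and period, and keep their absolute change in the absolute-change analyses.
- State before unblinding how a zero-baseline subject is classed for the 30% and 50% responder flags, for example as a non-responder because no reduction is possible.
- Note that near-zero baselines distort percentage change in the same way without any imputation: 0.2 rising to 2 is (2 - 0.2)/0.2 = 900%. Absolute change should therefore carry the interpretation.

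The cost is a few sentences in the SAP. The downside is that a rare record is missing from the secondary percentage-change analysis. The fix removes the invented divisor, but percentage change remains sensitive to small true baselines.
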